#### Sleep Measures:

Laboratory Polysomnography (PSG): Participants will be studied in our specially-equipped sleep laboratory at the JDDVAMC using a wireless PSG system (**Figure 1**, above). The recording will include a standard clinical PSG montage, including EEG, EOG and EMG for sleep staging, and respiratory effort and airflow for evaluation of sleep disordered breathing. In addition, end tidal PCO2 (PETCO2) will be measured to identify hypoventilation during sleep. Sleep parameters will be recorded continuously from bedtime to rise time on the night of PSG. Sleep and respiration will be scored using standard AASM criteria. The Apnea Hypopnea Index (AHI) will be computed as the number of apneas + hypopneas per hour of sleep. Sleep disordered breathing will be defined by an AHI≥5 events per hour of recorded sleep, using the AASM's standard scoring criteria.

Sleep Questionnaires: We will use the Insomnia Severity Index (ISI) to assess insomnia symptoms. The ISI is a 7-item instrument using Likert-type scales that measure perceived severity of insomnia symptoms from 0 (not at all) to 4 (very much). The ISI correlates well with the PSQI (r=.67), and sleep diary measures (r's=.32-.91). The Usability of Sleep Apnea Equipment-P (USE-SA(P) version 3.0) will be used to assess PAP usability at the 3-month follow-up. The self-administered questionnaire contains 18 items that measure 5 aspects of PAP equipment usability, including learnability, memorability, efficiency, device feedback, and satisfaction. An additional 7 items assess the frequency of usability issues, and 3 items ask about equipment features.

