
**Overview of sample size computations:** Power computations were performed using the Stata power command. To determine the required sample size for the study, we determined the hypotheses for which we require the largest sample size. In this study, Aim 2 requires the largest sample size (n=56 with complete data; N=62 total randomized). We conducted the power analysis for Aims 1 assuming the sample size of N=56 required to address Aim 2. Given the exploratory nature of Aim 3, these tests were not considered in determining the required sample size for the overall study.

4.6b. Data Analysis and Sample Size Calculation for Aim 1: This aim examines the efficacy of the BEST program on PAP adherence. The main outcome will be the proportion of nights (out of 30 nights) with >4 hours of PAP use, as measured by the PAP machine itself. PAP adherence will be computed for the first 30 days (month 1), and for each subsequent 30-day period (months 2-12). All participants will be measured for at least 180 days, thus providing at least 6 months of data for all participants. PAP adherence rates beyond month 6 will be computed for participants who enrolled early enough to provide such data. Because adherence data will be gathered remotely using existing telemonitoring technologies in which PAP machines transmit use data to a cloud-based server, complete data is expected for each person. In an ongoing VA-funded study of PAP adherence being conducted by [name] research group, PAP adherence data or confirmed non-use has been obtained in 100% of participants using this method. The proportion of nights a patient uses PAP for 4 or more house will be computed by summing nightly scores (1=PAP used at least 4 hours; 0=PAP used less than 4 hours) and dividing the sum by the number of observations (i.e., 30 nights). Denoting  $\hat{p}_{ij}$  as the proportion of nights for person "i" in month "j", the sampling distribution of  $\hat{p}_{ij}$  will have an expected value equal to  $p_i$  (the true proportion who use PAP in the population in month "i") and the standard deviation of this sampling distribution is equal to  $sqrt(N*p_i *(1-p_i))$ . Further, based on the central limit theorem the sampling distribution of these monthly proportions,  $\hat{p}_i$  is expected to be normally distributed, justifying the use of normal theory statistical methods for the analysis of monthly PAP adherence.

[figure not shown]

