**Data Analysis for Hypotheses 2a-d.** These hypotheses will be tested using ANCOVA models to compare groups (BEST vs. control) for each of main outcome measured at post-treatment, after adjusting for baseline measurement of the outcome as a covariate. Compared to a "split-plot ANOVA" or an analysis of change scores, this strategy offers greater statistical power and better controls for possible baseline differences.

**Power Analysis for Hypotheses 2a-d. Table 7** shows the required sample size as a function of the standardized effect size and the correlation between posttest and baseline scores to achieve 80% power using a two-tailed alpha of 0.05. Cohen describes an effect size of d=0.8 as large, d=0.5 as medium, and d=0.2 as small. **Table 7** focuses on the combination of effect sizes and pretest-posttest correlations that would achieve power of .80. To evaluate plausible pretest-posttest correlations for the measures associated with hypotheses 2a-c, we assessed baseline to 4-month follow-up measures in a RCT of a sleep intervention for Veterans with disabilities. These are presented in detail below for each of the three hypotheses. **Table 7** shows that under the most pessimistic scenario (assuming no correlation between pre-test and post-test measures), this study has sufficient power to detect a large effect (*d*=0.75). As the purpose of this study is to find clinically meaningful effects (i.e., effects that tend to be large), this power analysis suggests sufficient power to detect such effects for all outcome measures. However, our prior research found very substantial pretest/posttest correlations (e.g., r=.75) which would permit detection of smaller effects (i.e., medium effects of d=0.50). Using the lower confidence limits still found substantial correlations (e.g., r=0.56) suggesting that this study will have the ability to detect all effects of d=0.63 or larger with a sample size of n=56 with complete 3-month follow-up data. To achieve this, we will randomize 62 subjects into intervention vs. control.

**Table 7**. Required total sample size as afunction of effect size and pre-test/post-testcorrelation for 80% power, alpha=.05.

Sample	Effect Size	Pretest/Posttest
Size	(Cohen's d)	Correlation
	d=0.50 (medium)	r=0.75
N=56	d=0.55	r=0.68
N-50	d=0.60	r=0.60
	d=0.63	r=0.56

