Hypothesis 2d: The main respiratory function outcomes are PFTs (i.e., upright and supine respiratory function/forces) measured at 3-months. While we have no prior data on pretest/posttest correlations for these measures, our prior research has found a the SD for FVC when measured sitting is 17.1, and 15.7 when supine. Considering a 12% change as clinically relevant, this implies an improvement, expressed as Cohen's d=.70 (sitting, 12/17.1) and d=.76 (supine 12/15.7). **Table 7** shows that there would be sufficient power to detect a 12% improvement in sitting respiratory function (corresponding to d=.70) given a correlation of r=.36 in from baseline to 3 months. Likewise, there would be sufficient power to detect a 12% improvement in supine respiratory function (corresponding to d=.76) regardless of the size of the correlation.

4.6d: Analysis plan for Exploratory Aim 3: This aim considers whether the BEST program is more effective for subgroups of patients such as those with depression, insomnia or bladder dysfunction. For categorical measures, grouping variables will be coded as 0/1. For continuous measures (such as ISI score), participants will be categorized into groups, using clinical cutoffs. If such cutoffs yield highly imbalanced groupings, we will consider a median split. For a given variable, each grouping variable will be interacted with treatment group and introduced into each analysis described in Aims 1 and 2. The test of the interaction will assess whether the treatment is more effective for one subgroup than another.

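### Exploratory Aim 3 tests continuous moderators only after cutting them into groups; under stated assumptions this loses about 36% to 51% of the interaction information

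*Protocol*

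**What the plan says.** Section 4.6d of the Protocol is the only description of the Aim 3 analysis. For moderators measured on a scale: "For continuous measures (such as ISI score), participants will be categorized into groups, using clinical cutoffs". The fallback follows: "If such cutoffs yield highly imbalanced groupings, we will consider a median split". Then "each grouping variable will be interacted with treatment group and introduced into each analysis described in Aims 1 and 2", and the purpose is stated as: "The test of the interaction will assess whether the treatment is more effective for one subgroup than another".

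No cutoff, number of groups or definition of excessive imbalance is given. Two groups are explicit only for the median split; for the clinical cutoffs, two is implied by the comparison of one subgroup with another.

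The one named example is close to continuous. Under Sleep Measures, "The ISI is a 7-item instrument using Likert-type scales", with each item scored 0 to 4, so the total runs from 0 to 28. Table 6 shows that it is collected at baseline.

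On sizing, section 4.6 says: "Given the exploratory nature of Aim 3, these tests were not considered in determining the required sample size for the overall study". The trial is sized on Aim 2, at 56 patients with complete data and 62 randomized. The SAP covers Aims 1 and 2 only.

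**The concern.** A treatment-by-moderator interaction is among the least powerful tests that a two-arm trial of this size can run. Replacing a graded score by group membership treats all patients on one side of the cut as alike and discards the differences among them, although the full score has already been collected.

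The fallback adds a second problem. Its trigger has no number, and the text says only that a median split will be considered, so the final cut is settled after the moderator's distribution has been seen. A sample median also defines groups that belong to this sample and have no fixed clinical meaning outside it.

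At stake is how much Aim 3 can say about who benefits more. A non-significant interaction would be weak evidence at this sample size in any case, and cutting the score makes it weaker without need.

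**Working it through.** **1. The plan's own figure.** The documents give no power or information figure for Aim 3. The nearest stated figure is the Aim 2 size in Table 7, set "to achieve 80% power using a two-tailed alpha of 0.05", with the claim that the study can "detect all effects of d=0.63 or larger with a sample size of n=56". Per-arm size for ANCOVA, normal approximation:

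n = 2 × (1.960 + 0.842)² × (1 − r²) / d²

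- d = 0.63, r = 0.56: 2 × 7.849 × 0.6864 / 0.3969 = 27.1, so 28 per arm and N = 56.
- d = 0.75, r = 0: 2 × 7.849 / 0.5625 = 27.9, so again N = 56.

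The other Table 7 rows also give 56 (58 with the t distribution). N = 56 is therefore a fair base for what follows.

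**2. Information kept after cutting.** Assumptions, none of which the documents state: a normally distributed moderator, a linear interaction, two groups, and 1:1 allocation unrelated to the moderator. With a proportion p on one side of the cut, z_p the corresponding normal quantile and φ the normal density:

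efficiency = φ(z_p)² / [p(1 − p)]

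| Split | Calculation | Kept | Lost | 56 patients act like |
|---|---|---|---|---|
| 50/50 | 0.3989² / 0.25 | 0.637 | 36% | 36 |
| 70/30 | 0.3477² / 0.21 | 0.576 | 42% | 32 |
| 80/20 | 0.2800² / 0.16 | 0.490 | 51% | 27 |
| 90/10 | 0.1755² / 0.09 | 0.342 | 66% | 19 |

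The percentages do not depend on N. With all 62 randomized patients, the equivalents at 50/50 and 80/20 are about 39 and 30. An 80/20 split of 56 leaves about 11 patients in the smaller group, 5 or 6 per arm.

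**3. The same loss as power.** Take an interaction large enough for 80% power on the continuous score, so a noncentrality of 2.80. After cutting, it becomes 2.80 × √efficiency:

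- 50/50: 2.80 × 0.798 = 2.23, power about 61%.
- 70/30: 2.80 × 0.759 = 2.13, power about 57%.
- 80/20: 2.80 × 0.700 = 1.96, power about 50%.

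These are large-sample values. A simulation at N = 56 (8,000 runs per setting), with the continuous test at about 80%, gave 58% for a median split and 44% for an 80/20 split.

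**4. How far the range moves if the assumptions change.**

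- Uniform moderator: efficiency is 3p(1 − p), so the loss is 25% at 50/50 and 52% at 80/20.
- Normal moderator in three equal groups, scored as a trend: loss about 21%.
- Effect that truly steps at the median of a normal score: the roles swap. The linear test then has efficiency 2/π = 0.637, and where the grouped test has 80% power the linear test has about 61%.

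**5. What interactions the trial can see at all.** For a 0/1 moderator split 50/50 at N = 56, the standard error of the interaction is √[4 / (56 × 0.25)] = 0.535 SD. The interaction detectable with 80% power is 2.80 × 0.535 = 1.50 SD, or 1.50 × √(1 − 0.56²) = 1.24 SD with baseline adjustment at r = 0.56.

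For a smaller, assumed subgroup difference of 0.5 SD, under the linear and normal assumptions of step 2:

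| | Median split | Continuous score |
|---|---|---|
| Unadjusted | 16% | 22% |
| Adjusted, r = 0.56 | 20% | 29% |

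**The case against.** The strongest reply has five parts.

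- **The loss is not a property of this plan.** It depends on a distribution, a shape and a split that the documents do not give. This stands. A reader might infer that Aim 3 as written throws away 36% to 51% of its information; the documents do not support that as a fact, and 51% is not an upper limit.
- **Clinical groups match the question.** Aim 3 names patients with depression, insomnia or bladder dysfunction, and defined groups are a legitimate way to ask about them. This stands in part. It supports reporting effects on either side of a clinical cutoff. It does not support making the cut score the only test, and it does not support a median split.
- **The fallback is not outcome-driven.** A reader might infer that the cut could be chosen to produce a significant interaction. The text does not support that: the stated trigger is imbalance in the groups, which depends on the moderator and not on outcomes, and the rule is written in advance. Moving from 80/20 to the median would even raise efficiency from 0.49 to 0.64. What remains is the missing threshold and the non-committal wording.
- **The continuous test is also weak.** This stands. For a 0.5 SD subgroup difference, step 5 shows a gain of 6 to 9 percentage points, and a null result would be uninformative by either method. The drop of about 20 points in step 3 applies only to very large interactions.
- **Aim 3 is exploratory and unpowered.** True, and it limits the stakes. It explains low power, but it is no reason to prefer the method that uses less of the data already collected.

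**Conclusion.** The point holds in a limited form. The only planned Aim 3 test for continuous moderators uses a categorised score, with an open-ended median-split fallback, and neither document plans an interaction with the score itself. Given a roughly normal moderator, a linear interaction and two groups, the loss is about 36% for a median split and 51% for an 80/20 split. It differs under other distributions or splits and can reverse if the effect truly steps at the cutoff.

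A reader might infer that the trial's main conclusions are weakened. They are not: the Aim 1 and Aim 2 comparisons and the planned 62 patients are untouched. This is an inexpensive improvement to an exploratory analysis. It would not make Aim 3 well powered.

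**What to change.** Reword section 4.6d, and carry the same text into the SAP if Aim 3 is to be analysed:

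1. For continuous moderators, make the interaction of treatment with the continuous baseline score the main Aim 3 test in each Aim 1 and Aim 2 model. ISI is the named case. Baseline PHQ-9 would be treated the same way if it is the measure of depression, which 4.6d does not say.
2. Prespecify the clinical cutoff for each score and report the model-estimated treatment effect below and above it, as description. The clinical-cutoff interaction may stay as a secondary analysis, which also covers the possibility of a step.
3. Delete the median-split fallback.
4. Keep 0/1 coding for moderators that are truly categorical.

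The cost is wording only: no extra patients, visits or measurements, since ISI and PHQ-9 are already collected at baseline. The downside is the assumed linear interaction. A plot of outcome against score by arm should accompany the test, but at this sample size it is only a weak check on shape. The report should also say that interaction power is low by either method.

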### 5. Dissemination Plan

**5.1. Dissemination to the Scientific Community:** We intend to present the results of this study at national conferences on sleep and SCI/D, and to publish the results in peer-reviewed scientific journals. When possible, we will also take advantage of opportunities for dissemination of these findings available through VA Centers focused on SCI/D (e.g., VA HSR&D QUERI Center), such as in newsletters and lecture series.

**5.2.** Dissemination to VA providers: We anticipate that results will show the BEST program is effective in improving PAP adherence and that treatment of SDB will improve multiple patient outcomes. In that case, there will be immediate impact of the results on clinical care at our facility, as the BEST program can immediately become part of routine care for our SCI/D patients. We will also seek additional funding for a multi-site trial. We anticipate that such a trial would first focus on facilities with sleep medicine providers and SCI/D clinics. At the conclusion of this line of research, we will have a well-developed, useful clinical approach to managing SDB among SCI/D patients. We have employed the RE-AIM framework in designing and developing this treatment study making the likelihood of "clinical update" more feasible. Using this framework, we have designed a program that can ultimately be used in clinical settings.

We will also disseminate findings through the VA Sleep Network. In discussing this project at a national meeting of VA Sleep Providers in 2014, there was a great deal of interest from Centers in participating in a future multisite trial, as many recognize the challenges associated with treatment of SDB these patients.

## 6. Project Management:

6.1. Project Timeline: The proposed project will be carried out over a 3.25-year period (see GANTT, below).

	Year 1				Year 2							Year 3									
Quarters	1		2		3	4	4	1		2		3	4	1	1		2	3	3	4	1
Start-up Phase																					
Obtain list of SCI patient from Detroit																					
Obtain list of SCI patient from Ann Arbor																					
Obtain list of SCI patient from Cleveland																					
Recruitment letter & telephone screening																				П	
Enrollment & baseline assessments																				П	
Randomization																				П	
Intervention																				П	
3-month follow-up assessment																				П	
6-month PAP adherence monitoring																					
additional PAP adherance monitoring				Ι		Π															
Data analysis		Τ	Π	Π		Π	Π	Τ	Π	Π		Π	Π	Π	Π	Π					

## 6.2. Coordination across sites:

Human subjects activities will be carried out at JDDVAMC in Detroit, MI where Drs. [name] and [name] are based. They will oversee day-to-day operations and supervise staff. Drs. [name], [name] and [name] are based at VAGLAHS. Drs. [name], [name] and [name] will participate in [name] monthly research team meetings by phone or video conference, and Drs. [name], and [name] will travel to Detroit for investigators' meetings. [name] will play an ongoing role in weekly oversight of the patient education component of the BEST program. She has served in this consultative role through VA's Evidence Based Psychotherapy dissemination programs, and for other VA-funded research projects. Since the study statistician is based at VAGLAHS, we will use established procedures for secure data transfer between sites (e.g., shared network drive), and we will follow all current VA Policies regarding data transfer and security. We have experience transferring data between the two sites in accordance with VA regulations for previously conducted analyses.

Does Treatment Of Sleep-Disordered Breathing Improve Functional Outcomes In SCI?

Data Analysis Plan

NCT02830074

Approved Date April 2, 2020

DATA ANALYSIS PLAN

Data analysis plan for primary outcomes:

Data Analysis for Aim 1: This aim examines the effects of the BEST program on PAP adherence. The main outcome will be the number of nights (out of 90 nights) with >4 hours of PAP use (measured by the PAP machine itself). Hypothesis 1 will be assessed using a two-sample t-test to compare PAP use for the BEST program vs. control program. Because adherence data will be gathered remotely using telemonitoring technologies in which PAP machines transmit use data to a cloud-based server, complete data is expected for each person.

Data analysis for Aim 2: This aim compares outcome measures assessed at 3-months that are expected to improve as a result of the BEST program. These outcomes will be -- 1) Subjective Sleep Quality Measured by The Pittsburgh Sleep Quality Index (PSQI); 2) Quality of Life as Measured by WHO-QOL BREF Questionnaire, 3) Respiratory Function: Spirometry and Respiratory Muscle Force, 4) Functional Status as Measured by CHART Questionnaire, 5) Depressive Symptom Severity as measured by the Patient Health Questionnaire-9 (PHQ-9); 6) Fatigue Symptoms as measured by Flinders Fatigue Scale; 7) Sleepiness as measured by the Epworth Sleepiness Scale. For each outcome measure, a two-sample t-test will be used to compare PAP use for the BEST program vs. control program.

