Mixed-effects models will be used to compare monthly PAP adherence rates for the BEST program versus control program. When applied to longitudinal designs, mixed-effects models accommodate incomplete data across time points (such as arises in this study where only some participants will have data beyond six months) and can permit specification of a wide variety of residual covariance structures. PAP adherence will be analyzed using a 2 by 12 factorial mixed-effects model with a fixed intercept, where treatment group is a two-level between subjects factor (i.e., BEST versus control) and time is a 12 level categorical repeated measures factor (i.e., month 1, month 2, ... month 12). This approach will allow us to examine potential non-linear trends in the data which would not be readily apparent if time were treated as a continuous variable. The Bayesian Information Criteria (BIC) will be used to identify and select the best fitting residual covariance structure. Using the mixed-effects model, the difference in adherence rates between the BEST program and control group will be assessed and tested at each month.

Hypothesis 1a will be assessed evaluating the significance of the difference in adherence rates between the BEST program and control groups in months 1-3 (during the BEST program intervention).

Hypothesis 1b will be assessed by testing the significance of the difference in adherence rates between the BEST program and control groups in months 4-6 (after the BEST program has ended).

**Figure 6** illustrates four possible patterns of results Pattern 1 suggests the BÉST program immediately improved PAP adherence and effects were sustained over time. Pattern 2 shows that the BEST program improved PAP adherence during the treatment period; however, effects later diminish. Pattern 3 shows that the

BEST program improved PAP adherence gradually during the "treatment" period and effects were sustained over time. Pattern 4 also shows that the BEST program improved PAP adherence gradually; however, effects later diminished, These patterns will be statistically dissected to distinguish between immediate vs. gradual gains in pap adherence during the "treatment" phase, and between "sustained" and "diminishing" effects during the posttreatment phase (refer to [name] 2012).

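### Aim 1 has two main outcomes and two tests for months 1-3, and the SAP does not say whether hypotheses 1b and 1c still stand

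*SAP*

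**What the plan says.** Protocol section 4.6b states: "The main outcome will be the proportion of nights (out of 30 nights) with >4 hours of PAP use". Adherence is computed for month 1 and for each later 30-day period up to month 12. It is analysed in a mixed-effects model with two groups and twelve categorical months, in which "the difference in adherence rates between the BEST program and control group will be assessed and tested at each month". Hypothesis 1a concerns months 1-3, while the program runs. Hypothesis 1b, on the period after the program ends, "will be assessed by testing the significance of the difference in adherence rates between the BEST program and control groups in months 4-6". Hypothesis 1c covers months 6-12. On follow-up, 4.6b says: "All participants will be measured for at least 180 days, thus providing at least 6 months of data for all participants". Beyond month 6, only participants who enrolled early enough contribute.

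The protocol's Main Outcome Measures section instead takes the proportion of 90 nights with at least 4 hours of use as the main measure of PAP use.

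The SAP (approved April 2, 2020; protocol April 4, 2019) is headed as covering primary outcomes. Its Aim 1 main outcome is the number of nights out of 90 with more than 4 hours of use, and "Hypothesis 1 will be assessed using a two-sample t-test to compare PAP use for the BEST program vs. control program". It mentions no monthly periods, no mixed model, no 1b or 1c, and nothing after night 90. It does not say that it supersedes 4.6b.

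**The concern.** A reader cannot tell which analysis decides Aim 1. For the same three months there is a 90-night outcome with a t-test and a 30-night outcome with a mixed model. Unless one is fixed in advance, the choice could be made after the data are seen.

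The status of 1b is equally unclear. It asks whether adherence lasts once support stops, and section 4.6b sets out to tell sustained from diminishing effects. A total over nights 1-90 cannot do that. Going back to 4.6b unchanged is not a full answer either, because it tests every month and gives no rule for when 1a, 1b or 1c has succeeded.

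**Working it through.** **1. The three statements side by side**

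| Place | Main outcome | Window | Test |
|---|---|---|---|
| Protocol, Main Outcome Measures | proportion of nights, at least 4 h | 90 nights | none given there |
| Protocol 4.6b | proportion of nights, more than 4 h (scoring rule in the same section: at least 4 h) | each 30-night month, 1 to 12 | 2 by 12 mixed model |
| SAP, Aim 1 | number of nights, more than 4 h | 90 nights | two-sample t-test |

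Count against proportion is immaterial, because the denominator is fixed at 90. The window, the test and the wording of the threshold do differ.

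**2. Coverage of the hypotheses**

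90 nights = 3 × 30, which is months 1-3 and so hypothesis 1a only. Months 4-6 (nights 91-180) and months 6-12 lie outside the SAP outcome.

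**3. Which outcome the stated power belongs to**

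Inputs from 4.6b: SD = sqrt(0.5 × 0.5/30) = 0.0913, alpha 0.05, power 0.80. From 4.6a: 28 per group with complete data. Two-sided testing is stated for Aim 2 and assumed here. The standard error of the difference is 0.0913 × sqrt(2/28) = 0.0244. With the noncentral t on 54 degrees of freedom:
- detectable difference at 80% power: 0.0696 (plan: 7%)
- power for 10 points: 0.981 (plan: .98)

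The plan's figures reproduce, for one 30-night month. The same SD rule applied to 90 nights gives sqrt(0.25/90) = 0.0527 and a detectable difference of 0.040, or 0.040 × 90 = about 3.6 nights. The documents state no power for the 90-night outcome.

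**4. Hypothesis 1a read as one contrast**

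For each person, the 90-night proportion is (p1 + p2 + p3)/3, the mean of the three monthly proportions. If months 1-3 are complete, as both documents expect, and the model has a free mean for each group and month, the average months 1-3 contrast equals the difference in 90-night means. A simulated random-intercept model with dropout only after month 6 gave 0.1125 both ways. On this reading the estimate agrees with the SAP's, and only the standard error may differ.

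**5. Hypothesis 1a read as three monthly tests**

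The chance of at least one false positive in three two-sided tests at 0.05 depends on the correlation between months, which the documents do not give. At correlation 0 it is 1 − 0.95³ = 0.143. Simulated values for positive correlations (equal correlation to first-order autoregressive):

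| Assumed correlation | Chance of at least one false positive |
|---|---|
| 0.5 | 0.125 to 0.129 |
| 0.8 | 0.099 to 0.103 |
| 0.9 | 0.084 to 0.088 |
| 0.95 | 0.074 to 0.077 |

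Every value exceeds 0.05.

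**The case against.** The best defence is that the SAP limits itself to primary outcomes and withdraws nothing. On that view 1b and 1c remain where they were, with a model, windows and data in 4.6b, and the single hypothesis in the SAP is simply the primary one. Two of the three statements, including the latest, agree on 90 nights, and 1a can be read as one contrast whose estimate matches the SAP's.

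Much of this stands, and it rules out some stronger readings:
- A reader might infer that the SAP has replaced 4.6b, that the trial can no longer answer 1b, and that 90 of the 180 guaranteed nights go unanalysed. This follows only if the SAP is exclusive, and no text says so.
- A reader might take 1a to be three tests. The monthly-testing sentence supports this but does not settle it.
- A family-wise error figure for all twelve months would be out of place, since no hypothesis claims success on any one month of twelve.
- The six-month SD-card download at Visit 6 does not show that the visit exists only for 1b. The protocol does not say which nights the download serves, and it expects later adherence data from remote monitoring.

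The defence does not remove the conflict. The SAP never calls 1b and 1c secondary or says that 4.6b still applies, and for months 1-3 it names a different main outcome and a different test.

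**Conclusion.** The concern holds as an unresolved conflict over the main Aim 1 analysis, together with missing statements on 1b and 1c. It does not show that the sustained-adherence question has been abandoned.

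On numbers, the conflict is modest. If 1a is one contrast, the two approaches give the same estimate when months 1-3 are complete. If it is three tests at 0.05, the false-positive chance is about 7% to 14%, resting on an assumed correlation from 0.95 down to 0. The stated power of .98 for 10 points belongs to the 30-night outcome and cannot be carried over to the SAP's outcome. This should be settled in writing before outcome data are compared by group.

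**What to change.** 1. In the SAP and in 4.6b, name one primary outcome: the proportion of nights 1-90 meeting the 4-hour threshold, with one test at two-sided 0.05. That test is either the SAP's two-sample t-test or the months 1-3 average contrast from the mixed model, not both. Reconcile more than 4 hours with at least 4 hours.
2. State in the SAP that 1b is secondary, tested as one contrast of average adherence over months 4-6 from the protocol's mixed model. Testing it only if the primary test succeeds is a reasonable way to hold the error for the two tests at 0.05; the documents do not require that particular rule.
3. State that 1c is exploratory and reported as an estimate with a confidence interval, because only early enrollees supply data beyond month 6. Report the month-by-month differences the same way. Say where month 6 belongs, since the windows of 1b and 1c both include it.
4. Label the Aim 1 power statement as applying to one 30-night month, and restate it for the 90-night outcome. The 0.040 shown above uses the protocol's SD rule, which counts only night-to-night binomial variation. The restated figure should also allow for differences between participants, whose size the documents do not give.

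No new data or visits are needed. The cost is wording in both documents and one recalculation; separate monthly p-values and a formal test of 1c are given up.
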